16.4 Secondary Endpoints

- 16.41 Safety and tolerability data will be compiled. The maximum grade for each type of adverse event will be recorded for each patient, and frequency tables will be reviewed to determine patterns (by arm, disease and overall). Additionally, the relationship of the adverse event(s) to the study treatment will be taken into consideration. The rate of grade 3 or higher non-hematologic adverse events, and the rate of grade 4 or higher adverse event (hematologic and non-hematologic) will be computed each with a 95% exact binomial confidence interval.
- 16.42 Summary statistics for clinical benefit (mean and standard deviations for continuous variables and frequencies and percentages for discrete variables) will be compiled for hematologic improvements and transfusion requirements.
- 16.43 Duration of response is defined for all evaluable patients who have achieved a response as the date at which the patient's earliest best objective status is first noted to be a CR/CRi response to the earliest date progression is documented. If a patient dies subsequent to the response without a documentation of disease progression, the patient will be censored at the last date disease was assessed. In the case of a patient failing to return for evaluations before a documentation of disease progression, the patient will be censored for progression on the date of last evaluation. The distribution of duration of response will be estimated using the method of Kaplan-Meier (1958).
- 16.44 Time to response/progression is defined as the time from registration to the earliest date of documentation of response/disease progression. If a patient dies without a documentation of disease progression the patient will be censored at the last date disease was assessed. In the case of a patient starting treatment and then never returning for any evaluations, the patient will be censored for progression 1 day post-registration. The distribution of time to progression will be estimated using the method of Kaplan-Meier (1958).
- 16.45 Survival time is defined as the time from registration to death due to any cause. The distribution of survival time will be estimated using the method of Kaplan-Meier (1958).
- 16.46 Time to AML or death is defined for all evaluable patients with MDS and MF as the time from registration to leukemic transformation or death due to any cause. The distribution of time to AML or death will be estimated using the method of Kaplan-Meier (1958).
- 16.5 Exploratory Analysis
- An exploratory analysis will be conducted, if there is indication, to determine any differences in study endpoints for subgroups of patients within each treatment arm as defined by the grouping factors (section 5.0), descriptive factors (section 12.0), dose level or any other patient demographics.
- 16.6 Correlative Research
- 16.61 Statistical analysis of pharmacokinetics and biomarkers will be primarily descriptive. Continuous biomarker levels will be explored in a graphical manner

including mean plots and plots of change and percent change from baseline and other summary measures. Any potential relationships between the baseline level or change in the level of each biomarker and clinical outcome such as overall response, 6-month progression and survival, and adverse event incidence will be further analyzed using Wilcoxon rank sum tests or logistic regression methods, as appropriate. Association between a dichotomized biomarker and overall response will be assessed using a chi-squared test. Comparisons with 1-sided p-values ≤ 0.10 are considered significant. As this correlative component is exploratory in nature, we have not adjusted for multiple comparisons.

- 16.62 Patient-reported outcomes will be assessed at baseline, cycles 3, 6, 9, and EOS.. MPN-SAF TSS was created to address the constellation of symptoms. The MPN-SAF includes 1 item measuring fatigue from the previously validated Brief Fatigue Inventory (BFI), as well as linear analog scales capturing early satiety, abdominal discomfort, inactivity, concentration problems, numbness/tingling in the hands/feet, night sweats, itching, bone pain, fever, and weight loss. The MPN-SAF TSS has previously been validated for use at a single time point by co-administration with previously validated instruments.

Quality of life will be assessed prior to review of treatment response and discussions of patient's general health since last treatment evaluation. QOL will be measured using the EORTC QLQ-C30, a 30-item patient-reported questionnaire about patient ability to function, symptoms related to the cancer and its treatment, overall health and quality of life, and perceived financial impact of the cancer and its treatment. 28 of the 30 items are measured on a 1-4 scale (1=not at all; 4=very much) with the remaining two items (overall health and overall quality of life) scored on a 1-7 numeric analogue scale (1=very poor; 7=excellent). The recall period for the EORTC QLQ-C30 is one week. The EORTC QLQ-C30 is the product of more than a decade of collaborative research and to date, more than 2200 studies using the EORTC QLQ-C30 have been registered with the EORTC (Fayers et al, 2001 [EORTC Scoring Manual]). The patient booklet containing this questionnaire will be administered to all willing patients via a paper booklet in clinic at baseline and on day 1 of every cycle starting with Cycle 2, and will be scored according to the published scoring algorithms.

Scale score trajectories over time and changes from baseline over time will be examined using repeated measures or growth curve models, as appropriate, stream plots and mean plots with standard deviation error bars overall. Scores and changes at each cycle will be statistically tested using paired t-tests, and standardized response means (i.e. effect sizes) (mean of the change from baseline scores at a given cycle, divided by the standard deviation of the change scores) will be interpreted (after applying Middel's (2002) adjustment) using Cohen's (1988) cut-offs: <0.20 = trivial; 0.20 - <0.50 = small; 0.50 - <0.80 = moderate; and ≥ 0.80 = large.

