10.0 Safety and Adverse Events

10.1 Unanticipated Problems Involving Risk to Subjects or Others

Any incident, experience, or outcome that meets all of the following criteria:

- Unexpected in nature, severity, or frequency (i.e. not described in study-related documents such as the IRB-approved protocol or consent form, the investigators brochure, etc)
- Related or possibly related to participation in the research (i.e. possibly related means there is a reasonable possibility that the incident experience, or outcome may have been caused by the procedures involved in the research)
- Suggests that the research places subjects or others at greater risk of harm (including physical, psychological, economic, or social harm).

Adverse Event

An **adverse event** (AE) is any symptom, sign, illness or experience that develops or worsens in severity during the course of the study. Intercurrent illnesses or injuries should be regarded as adverse events. Abnormal results of diagnostic procedures are considered to be adverse events if the abnormality:

- results in study withdrawal
- is associated with a serious adverse event
- is associated with clinical signs or symptoms
- leads to additional treatment or to further diagnostic tests
- is considered by the investigator to be of clinical significance

Serious Adverse Event

Adverse events are classified as serious or non-serious. A **serious adverse event** is any AE that is:

- fatal
- life-threatening
- requires or prolongs hospital stay
- results in persistent or significant disability or incapacity
- a congenital anomaly or birth defect
- an important medical event

Important medical events are those that may not be immediately life threatening, but are clearly of major clinical significance. They may jeopardize the subject, and may require intervention to prevent one of the other serious outcomes noted above. For example, drug overdose or abuse, a seizure that did not result in in-patient hospitalization, or intensive treatment of bronchospasm in an emergency department would typically be considered serious.

All adverse events that do not meet any of the criteria for serious should be regarded as **non-serious adverse events**.

Adverse Event Reporting Period

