The study period during which adverse events must be reported is normally defined as the period from the initiation of any study procedures to the end of the study treatment follow-up. For this study, the study treatment follow-up is defined as 30 days following the last administration of study treatment.

Preexisting Condition

A preexisting condition is one that is present at the start of the study. A preexisting condition should be recorded as an adverse event if the frequency, intensity, or the character of the condition worsens during the study period.

General Physical Examination Findings

At screening, any clinically significant abnormality should be recorded as a preexisting condition. At the end of the study, any new clinically significant findings/abnormalities that meet the definition of an adverse event must also be recorded and documented as an adverse event.

Post-study Adverse Event

All unresolved adverse events should be followed by the investigator until the events are resolved, the subject is lost to follow-up, or the adverse event is otherwise explained. At the last scheduled visit, the investigator should instruct each subject to report any subsequent event(s) that the subject, or the subject's personal physician, believes might reasonably be related to participation in this study. The investigator should notify the study sponsor of any death or adverse event occurring at any time after a subject has discontinued or terminated study participation that may reasonably be related to this study. The sponsor should also be notified if the investigator should become aware of the development of cancer or of a congenital anomaly in a subsequently conceived offspring of a subject that has participated in this study.

Abnormal Laboratory Values

A clinical laboratory abnormality should be documented as an adverse event if any one of the following conditions is met:

- The laboratory abnormality is not otherwise refuted by a repeat test to confirm the abnormality
- The abnormality suggests a disease and/or organ toxicity
- The abnormality is of a degree that requires active management; e.g. change of dose, discontinuation of the drug, more frequent follow-up assessments, further diagnostic investigation, etc.

Hospitalization, Prolonged Hospitalization or Surgery

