10.31 Adverse Event Characteristics

CTCAE term (AE description) and grade: The descriptions and grading scales found in the revised NCI Common Terminology Criteria for Adverse Events (CTCAE) version 5.0 will be utilized for AE reporting. All appropriate treatment areas should have access to a copy of the CTCAE version 5.0. A copy of the CTCAE version 5.0 can be downloaded from the CTEP web [site](http://ctep.cancer.gov/protocolDevelopment/electronic_applications/ctc.htm): (http://ctep.cancer.gov/protocolDevelopment/electronic_applications/ctc.htm)

10.311 Adverse event monitoring and reporting is a routine part of every clinical trial. First, identify and grade the severity of the event using the CTCAE version 5.0. Next, determine whether the event is expected or unexpected (see Section 10.2) and if the adverse event is related to the medical treatment or procedure (see Section 10.3). With this information, determine whether the event must be reported as an expedited report (see Section 10.4). Expedited reports are to be completed within the timeframes and via the mechanisms specified in Section 10.4. All AEs reported via expedited mechanisms must also be reported via the routine data reporting mechanisms defined by the protocol (see Sections 10.6 and 18.0).

10.312 Each CTCAE term in the current version is a unique representation of a specific event used for medical documentation and scientific analysis and is a single MedDRA Lowest Level Term (LLT). Grade is an essential element of the Guidelines and, in general, relates to **severity** for the purposes of regulatory reporting to NCI.

NOTE: A severe AE, as defined by the above grading scale, is **NOT** the same as serious AE which is defined in the table in Section 10.4.

10.313 Medical conditions/diseases present before starting study treatment are only considered adverse events if they worsen after starting study treatment (any procedures specified in the protocol). Adverse events occurring before starting study treatment but after signing the informed consent form are not recorded. Abnormal laboratory values or test results constitute adverse events only if they induce clinical signs or symptoms or require therapy, and are recorded.

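### Section 10.313 contradicts 10.1, 10.8 and 10.61 on when a new low blood count is an adverse event, so the 16.41 Grade 4 or higher rate depends on the rule followed; nor does 16.41 relate worst grade to baseline

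*Combined protocol and SAP*

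**What the plan says.** Section 16.41 summarizes safety by worst grade: "The maximum grade for each type of adverse event will be recorded for each patient", with frequency tables by arm, disease and overall. It then gives two rates with intervals. One is for Grade 3 or higher non-hematologic events. For the other, "the rate of grade 4 or higher adverse event (hematologic and non-hematologic) will be computed each with a 95% exact binomial confidence interval".

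Section 10 decides what counts as an adverse event, in several places:

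- **10.1, general definition:** "any symptom, sign, illness or experience that develops or worsens in severity during the course of the study".
- **10.1, abnormal diagnostic results:** several grounds are listed, one being that the result "is considered by the investigator to be of clinical significance".
- **10.1, Abnormal Laboratory Values:** any one of three grounds is enough. The first is "The laboratory abnormality is not otherwise refuted by a repeat test to confirm the abnormality".
- **10.1, Preexisting Condition:** such a condition "should be recorded as an adverse event if the frequency, intensity, or the character of the condition worsens".
- **10.313, laboratory values:** "Abnormal laboratory values or test results constitute adverse events only if they induce clinical signs or symptoms or require therapy".
- **10.313, prior conditions:** "Medical conditions/diseases present before starting study treatment are only considered adverse events if they worsen after starting study treatment".
- **10.8, to which 10.2 refers for recording:** anemia, neutrophil decrease and platelet decrease are graded at baseline and at every evaluation, with no condition about symptoms or therapy.
- **10.61, Special Situations for Expedited Reporting:** Grade 3 and 4 neutrophil, white cell and platelet decreases and anemia, if not attributed to AZD1775 and not leading to hospitalization, need no expedited report but must still be reported routinely.

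**The concern.** The 10.1 laboratory rule sets out sufficient conditions, while 10.313 sets a necessary one. Both cannot hold for a confirmed low count without symptoms or treatment, and no text ranks them. Sections 6.22 and 6.23 provide for additional sites, so two sites could each follow the protocol and record the same patient differently.

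This matters because 16.41 is where hematologic toxicity is summarized for secondary goal 2.21. Section 1.41 lists anemia, neutropenia and thrombocytopenia as reactions to AZD1775, and 15.27 describes AraC as potently myelosuppressive. Section 7.4a leaves myelosuppression out of DLT apart from marrow hypoplasia beyond 42 days. The 16.8 monitoring rule uses the DLT criteria, so it largely leaves it out too.

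A second gap lies in the summary itself. Section 3.13 sets no floor for neutrophils, platelets or hemoglobin, so patients with disease-related Grade 4 counts can enter. Baseline grades are collected under 10.8, yet 16.41 plans nothing that sets worst grade against them. Its only Grade 4 or higher rate with an interval pools hematologic and non-hematologic events. Section 16.42 covers improvement and transfusion requirements, not worsening.

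**Working it through.** Section 16.41 states no numerical figure, so there is none to reproduce. The check is first of wording, then of possible size.

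**1. One test case under each rule.** Take a new Grade 4 neutropenia, confirmed on repeat, without symptoms and untreated. The case is realistic because Section 9 does not recommend routine G-CSF.

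| Rule | Is it an adverse event? |
|---|---|
| 10.1, laboratory values | Yes; not being refuted on repeat is enough |
| 10.1, diagnostic results | Depends on further tests or the investigator's judgment |
| 10.8 | Graded at every evaluation, no condition attached |
| 10.61 | Routinely reportable if not attributed to AZD1775 |
| 10.313 | No; no signs, symptoms or therapy |

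Section 10.313 is the outlier.

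**2. A stable Grade 4 count present at entry.** The general definition and the preexisting-condition rule in 10.1, and the worsening sentence in 10.313, all require a new or worsened condition. They agree, so an unchanged count is not an event.

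**3. Possible size of the rule conflict.** The documents give no cytopenia rates, so every rate here is an assumption. Only n = 20 evaluable per arm (16.23) comes from the plan. Let e be the share of patients with new Grade 4 neutropenia, u the share of those who are asymptomatic and untreated, and r the share of these omitted patients who have another Grade 4 or higher event.

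- Rate under the 10.1 laboratory rule = e
- Rate under 10.313 = e(1 − u)
- Single-lineage gap = e·u
- Pooled gap = e·u·(1 − r), since a patient with another Grade 4 or higher event is counted anyway

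With e = 0.5, the 10.1 rule gives 10/20 = 50% (exact 95% CI 27–73%). Under 10.313:

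| u | Rate (exact 95% CI) | Single-lineage gap | Pooled gap, r = 0.3 | Pooled gap, r = 0.6 |
|---|---|---|---|---|
| 0.3 | 7/20 = 35% (15–59%) | 15 points | 10.5 | 6 |
| 0.5 | 5/20 = 25% (9–49%) | 25 points | 17.5 | 10 |
| 0.7 | 3/20 = 15% (3–38%) | 35 points | 24.5 | 14 |

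With e and u each between 0.3 and 0.7, the single-lineage gap runs from 0.3 × 0.3 = 9 points to 0.7 × 0.7 = 49 points.

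**4. What a summary against baseline would add.** With stable Grade 4 counts excluded, patients who enter at Grade 4 in a lineage stay in the denominator but cannot have a new Grade 4 event there. Let p = 0.5 be the emergent rate among those at risk and b the share entering at Grade 4. The rate over all treated patients is p(1 − b): 40%, 30% or 20% for b = 0.2, 0.4 or 0.6. In the pooled rate these patients can have a Grade 4 event elsewhere, with probability q, so it is p(1 − b) + q·b. With q = 0.3 this gives 46%, 42% or 38%; with q = 0.5 it stays at 50%. The all-treated figure is a valid incidence. It simply answers a different question from emergence among those at risk.

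**The case against.** The strongest reply is that 10.1, 10.8 and 10.61 all point to capture, and the last two name these lineages. Reading the specific instruction over the generic closing sentence of 10.313 would remove most of the problem. That is a sensible reading, but the protocol does not adopt it, and 10.313 is worded as an exclusive condition. Central record review under 6.22 could impose one reading, but nothing says which.

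The conflict is also narrow. Section 9.2 provides blood product support, and a transfused anemia or thrombocytopenia meets the therapy condition in 10.313. This stands, and it is why the point concerns chiefly neutropenia.

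A reader might infer that stable baseline Grade 4 counts inflate the rate. For example, take 20 patients: 10 at unchanged Grade 4, 3 newly at Grade 4 without symptoms or therapy, and 2 newly at Grade 4 needing therapy. Counting every graded value gives 15/20 = 75%. The documents do not support that: the worsening rules exclude the 10, and 10.8 is a grading schedule that does not cancel them. The contrast that remains is 5/20 = 25% (9–49%) under 10.1 against 2/20 = 10% (1–32%) under 10.313. Section 3.22 also excludes patients with toxicities persisting from prior AML treatment, which restricts some low counts at entry.

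The maximum-grade tables will show hematologic event types separately, by arm and disease. That is true, but they carry no baseline grade and inherit the same recording conflict. One could also read the word each in 16.41 as promising separate hematologic and non-hematologic rates; it more naturally refers to the two rates just named.

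Finally, the low weight on cytopenia is deliberate, as 1.52 and 7.4a show. That explains the DLT definition. It does not justify a planned safety rate whose numerator is undetermined.

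**Conclusion.** The concern holds as a minor point. Section 10.313 contradicts the 10.1 laboratory rule and the routine capture in 10.8 and 10.61, so a new, asymptomatic, untreated Grade 4 count may or may not enter the 16.41 rate. Separately, 16.41 gives no summary of worst grade against baseline and no hematologic Grade 4 or higher rate of its own with an interval.

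The size is conditional throughout. At an assumed 50% rate of new Grade 4 neutropenia, the gap is 15 to 35 points for that lineage and about 6 to 25 points in the pooled rate that is actually planned. Other inputs would move these figures, and the conflict has no effect where every such patient has symptoms, needs therapy or has another Grade 4 event.

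Two further inferences would go too far. The all-treated denominator is not an error. Nor is any primary or safety decision rule affected: the primary analysis, the DLT definition and the 16.8 boundaries are unchanged, and under 16.23 adverse event data may inform the choice between Arms B and C only when both arms pass and the response difference is below 10%.

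**What to change.** 1. For blood counts, replace the laboratory sentence in 10.313 with one rule: any on-treatment worsening in CTCAE grade from baseline is an adverse event, regardless of symptoms or therapy.
2. Keep the pooled Grade 4 or higher rate over all treated patients, and also report hematologic and non-hematologic Grade 4 or higher rates separately, each with an exact 95% interval.
3. Add tables of baseline grade by worst grade for neutrophils, platelets and hemoglobin, by arm and disease.
4. As an optional supplement, give the per-lineage Grade 4 rate among patients below Grade 4 in that lineage at baseline, stating how many are left out.

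The cost is one clarification, a few lines in Section 16 and a few tables. Baseline counts, taken within 7 days before registration, and on-study counts are already collected under Section 4. The statistical cost falls only on the optional item, through wider intervals: at a 50% rate, 25–75% for 8/16 and 21–79% for 6/12, against 27–73% for 10/20.

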2.2 Secondary Goals

- 2.21 To determine the safety and tolerability of AZD1775 alone or combined with AraC in the study population.
- 2.22 To estimate additional measures of clinical benefit (i.e. hematological improvements, transfusion requirements, spleen size reduction).
- 2.23 To measure the duration of response of AZD1775 alone or combined with AraC.
- 2.24 To measure time to response of AZD1775 alone or combined with AraC.
- 2.25 To measure time to progression of AZD1775 alone or combined with AraC.

- 2.26 To measure overall survival of AZD1775 alone or combined with AraC.
- 2.27 To measure time to AML (for MDS, MF subjects) of AZD1775 alone or combined with AraC

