The following one-stage binomial design uses 21 patients to test the null hypothesis that the true CR/CRi response proportion in a given patient population is at most 15%.

Decision Rule: Enter 21 patients into the study. If 5 or fewer CR/CRi responses are observed in the first 21 evaluable patients, we will consider this regimen ineffective in this patient population. Otherwise, if 6 or more CR/CRi responses are observed in the first 21 evaluable patients, we may recommend further testing of this regimen in subsequent studies in this population. We anticipate accruing an additional 2 patients to account for ineligibility, cancellation, major treatment violation, or other reasons. Thus, the total maximum accrual to this arm is 23 patients.

Assuming that the number of CR/CRi responses is binomially distributed, the significance level within this arm is $\leq 10\%$ and the probability of declaring that this regimen warrants further studies (i.e., statistical power) under various

CR/CRi response proportions can be tabulated as a function of the true CR/CRi response rate as shown in the following table.

If the true CR/CRi rate is...	0.15	0.20	0.25	0.30	0.35	0.40
Then the probability of declaring that the regimen warrants further studies is...	0.08	0.23	0.43	0.64	0.80	0.90

- 16.23 Arm B and C: Efficacy and safety of AZD1775 in combination with AraC compared to AZD1775 alone in relapsed/refractory AML or HMA failure MDS and AML patients.

Statistical Design, Analysis and Decision Rule

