Efficacy and safety of AZD1775 alone or with AraC will be tested in patients with relapsed/refractory AML and patients with HMA failure MDS using a flexible randomized phase II selection design. Patients will be randomized to AZD1775 alone or with AraC in a 1:1 fashion using a dynamic allocation procedure (Pocock & Simon 1975). The primary endpoint will be the complete response rate, which will be defined as an objective status of CR or CRi. Complete response rate will be evaluated over all cycles of study treatment. The proportion of CR/CRi responses will be estimated by the number of CR/CRi responses divided by the total number of evaluable patients (by arm). Two-sided 95% confidence intervals will be computed using an exact binomial confidence interval. The frequency and relative frequency of individual response categories will also be computed. Estimates will also be computed by arm separately for each disease. For a subject to be considered evaluable for statistical analysis, the subject must be eligible, provide consent, initiate treatment and not experience a major treatment violation during the first cycle of treatment.

The selected design is a flexible randomized phase II selection design (Sargent & Goldberg 2001). This study will randomize 40 evaluable patients (20 per arm). The minimum required number of CR/CRi responses for an arm to be considered as having evidence of efficacy is 3 (out of 20 evaluable patients). This decision rule is based on a single-arm single-stage binomial design testing the null hypothesis that the true CR/CRi response proportion in a given arm is at most 5% (Tawfik et al. 2014, Giles et al. 2005, Jabour et al. 2010, Prevet et al. 2011) with the smallest CR/CRi response proportion warranting subsequent studies being 25%.

In the event that both arms meet this decision rule for efficacy, the combination arm will be considered as having additional efficacy over the single-agent arm if the CR/CRi response rate on the combination arm is at least 10% greater than the single-agent arm. If the difference is <10%, then the trial is considered statistically ambiguous and the selection between the combination and single-agent arm will be allowed to include other factors (e.g., adverse event data) in addition to the CR/CRi response rate. We anticipate accruing an additional 4 patients (2 patients per arm) to account for ineligibility, cancellation, major

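### Duration of response and time to progression censor deaths without documented progression, and no competing-risk or progression-or-death estimate stands beside them (secondary endpoints only)

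*Combined protocol and SAP*

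**What the plan says.** Measuring how long responses last is a stated secondary goal (2.23): "To measure the duration of response of AZD1775 alone or combined with AraC". Section 16.43 runs the clock from the first record of CR or CRi to the first documented progression and uses Kaplan-Meier. Where a responder "dies subsequent to the response without a documentation of disease progression, the patient will be censored at the last date disease was assessed".

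Section 16.44 has the same rule for time to progression, again with Kaplan-Meier: "If a patient dies without a documentation of disease progression the patient will be censored at the last date disease was assessed". It adds a rule for a patient who starts treatment and is not seen again: "never returning for any evaluations, the patient will be censored for progression 1 day post-registration". A patient who dies before any evaluation would fall under that rule.

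Two planned time-to-event endpoints count death as an event. Overall survival (16.45) applies to everyone. Section 16.46 applies to evaluable MDS and MF patients only and is "the time from registration to leukemic transformation or death due to any cause". Section 16.61 mentions progression and survival at six months as an exploratory biomarker outcome but does not define it as a composite. Section 16 names no progression-free, event-free or relapse-free survival and no cumulative-incidence analysis.

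**The concern.** A patient who dies in remission can no longer relapse, so death is a competing event. Kaplan-Meier treats that patient as someone who might still have progressed later. The resulting curve is not the share of responders alive and in response, and its complement is not the share who have progressed. It is too high as an estimate of progression incidence, because the patients removed by death are in effect redistributed over those still at risk.

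What is at stake is how two secondary, descriptive results are read. With few responders per arm, one or two deaths in remission would visibly change a curve that counted them and leave no step in the planned one. For the AML groups no other planned relapse- or progression-based endpoint shows those deaths.

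**Working it through.** The plan states no figure for duration of response, so there is none to reproduce. The scale comes from the design in 16.22 and 16.23.

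**Number of responders.** Arm A passes "if 6 or more CR/CRi responses are observed in the first 21 evaluable patients". For Arms B and C the minimum for "evidence of efficacy is 3 (out of 20 evaluable patients"). At the design rates:
- Arm A: 21 × 0.15 = 3.15 to 21 × 0.40 = 8.4 responders.
- Arms B and C: 20 × 0.05 = 1 to 20 × 0.25 = 5 responders each.

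**First event is a death in remission.** The planned curve has no step and stays at 1.00. The share alive in response is 1 − 1/6 = 0.833 with 6 responders and 1 − 1/3 = 0.667 with 3.

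**One death among 6 responders, all followed to an event.** Compare the curves when only half are alive in response, after the third event. Censoring is placed at the death date for simplicity.
- Death first: (4/5)(3/4) = 0.600.
- Death second: (5/6)(3/4) = 0.625.
- Death third: (5/6)(4/5) = 0.667.
- Death fourth, fifth or sixth: 0.500, because it has not yet happened.

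With all positions equally likely, the mean is (0.600 + 0.625 + 0.667 + 3 × 0.500)/6 = 0.565.

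**Both estimators on one data set.** Take 8 responders with hypothetical end times of 2, 3, 4, 5, 6, 8, 10 and 12 months, those at 2 and 5 being deaths in remission.
- Planned rule at 6 months: (6/7)(5/6)(3/4) = 0.536. The next step, ×(2/3), gives 0.357 at 8 months, so the median is 8 months.
- Deaths counted: 3/8 = 0.375 at 6 months, median 5 months.
- Progressed by 6 months: 3/8 = 0.375 in fact, against 1 − 0.536 = 0.464 from the planned curve.

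**Range over the missing input.** Let f be the share of first events that are deaths in remission. The documents do not give it, so the values below are assumptions, with independent constant hazards.
- Planned median divided by event-free median: 1/(1 − f).
- Alive in response at the planned median: 2^(−1/(1−f)).
- Cumulative incidence of progression at that time: (1 − f)(1 − 2^(−1/(1−f))).

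| f (assumed) | Median ratio | Alive in response (planned curve: 0.50) | Progressed (1 − KM: 0.50) |
|---|---|---|---|
| 0 | 1.00 | 0.500 | 0.500 |
| 0.1 | 1.11 | 0.463 | 0.483 |
| 0.2 | 1.25 | 0.420 | 0.464 |
| 0.4 | 1.67 | 0.315 | 0.411 |
| 0.5 | 2.00 | 0.250 | 0.375 |

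**Against sampling error.** With 6 responders and exponential times, the central 80% of simulated sample medians runs from 0.32 to 1.59 times the true median. At small f the effect lies inside that noise.

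**Limit of these figures.** The plan censors at the last assessment, which is earlier than the death date. That shifts the numbers somewhat. In a single small sample, a progression falling between a patient's last assessment and death can pull the planned curve down early. The death itself still produces no step.

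**The case against.** The strongest reply is that this is a choice of estimand and not an error. Censoring deaths in a time-to-progression analysis is a recognised convention, and the plan states it openly. The progression criteria for MDS and MF in 11.2 and 11.3 do not list death. Section 16.43 does not claim to estimate time alive in response, and the plan nowhere says that 1 minus Kaplan-Meier will be reported as an incidence. Overall survival captures every death, the endpoints are descriptive, and the numbers are small. All of this stands, and it is why the point is an improvement to secondary analyses and no more. What it does not answer is that nothing planned shows relapse or progression together with death. The MDS table in 11.2 does count death during treatment as failure, but that is a response category and does not enter the curves.

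A reader might go further in two ways that the documents do not support.
- *No disease group has a death-inclusive composite.* Section 16.46 provides one for MDS and MF. It fills the gap only partly: it starts at registration, covers all evaluable patients and not just responders, and counts leukemic transformation but not other progression or loss of response.
- *The censoring could tilt the choice between Arms B and C.* When the arms differ by less than 10%, 16.23 says selection "will be allowed to include other factors (e.g., adverse event data) in addition to the CR/CRi response rate". Adverse event data are the only factor named; use of duration of response would be conjecture. Section 10.8 records any death within 30 days of last treatment as a Grade 5 event regardless of attribution, and later deaths if at least possibly related, so many such deaths would count through the named factor.

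**Conclusion.** The point holds as a cheap improvement confined to 16.43 and 16.44. That deaths in remission cause no drop in the planned curve follows from the text. That 1 minus Kaplan-Meier overstates the incidence of progression follows from death being a competing event. The size cannot be derived from the documents: it is zero if no responder dies in remission, and every figure above beyond the responder counts rests on an assumed death share or a hypothetical sequence of events. The gap in planned endpoints is complete for the AML groups, which have overall survival alone, and partial for MDS and MF. The CR/CRi estimates and decision rules do not change.

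**What to change.** - **16.43.** Choose one of two routes. Either count death from any cause as an event alongside relapse or progression, and censor patients alive in response at their last disease assessment; or keep the current event and report the cumulative incidence of relapse or progression with death in remission as a competing event.
- **16.44.** Keep time to progression, but estimate it by cumulative incidence with death as a competing event. Count a death before the first evaluation as a competing event on its date instead of censoring it at day 1.
- **Reporting.** Give the number of responders and the number of deaths in remission beside each median.

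The cost is an amendment to Section 16.4 and slightly more analysis with standard estimators. Death dates are already needed for 16.45. If death is counted as an event, the reported medians will be shorter whenever deaths in remission occur.
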